8.5 Multicenter Studies

No per-center analyses are planned.

8.6 Adjustment for Covariates

Baseline value will be used as a covariate in the MMRM analyses for the co-primary endpoint ADAS-Cog11 score (see Section 8.3.7).

8.7 Examination of Subgroups

No subgroup analyses are planned for this study.

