# 3.1. Summary of Non-Clinical Findings

In APP transgenic AD mice, buntanetap led to a decrease in APP levels, improved neuronal stem cell survival and increased levels of brain-derived neurotrophic factor (BDNF) (Marutle 2007, Kadir 2008, Lilja 2013). Chronic administration of buntanetap to APP transgenic mice totally prevented decline in memory and learning as well as in long-term potentiation at brain and plasma concentrations that are 10 times lower than originally published (Teich 2018). In alpha-synuclein (αSYN) transgenic PD mice, buntanetap restored gut motility to normal and lowered aSYN in the brain and gut of the tg PD mice. Again, the efficacious levels were 10 times lower than originally published (Kuo 2019). In DS trisomic mice buntanetap fully restored axonal transport *in vitro* and *in vivo* (Chen 2020). In summary, buntanetap is a translational inhibitor of APP and aSYN and fully restores function at doses that are very low and very safe, and the plasma levels seen are attainable with low oral dosing in humans.

Buntanetap was not mutagenic or clastogenic as assessed by *in vitro* assays.

The cardiac electrophysiological properties of buntanetap tartrate were negative *in vitro* using human ether-a-go-go related gene (hERG) transfected human embryonic kidney cells (HEK 293). Buntanetap did not adversely affect the interval seen in an electrocardiogram (ECG) test (QT (or QTc)) interval.

Four-week toxicity studies in dogs showed brain toxicity (ataxia and tremors/twitching) and gastrointestinal (GI) toxicity at 30 mg/kg/day, which was dose-dependent and reversible. The no observed adverse effect level (NOAEL) was 20 mg/kg/day in dogs. The signs/symptoms noted at high doses of buntanetap may be related to cholinergic manifestations. In *in vitro* assays, buntanetap showed minimal inhibition of AChE or BChE (Butyrylcholinesterase) activity, however, a metabolic product of buntanetap, N1-norposiphen demonstrated acetyl cholinesterase inhibitory activity (Yu 2013). There were no effects on the reproductive organs associated with 4-week exposure to buntanetap in male or female rats or dogs.

Repeat Oral dose Toxicity Study of buntanetap in male and female rats giving 10, 20 and 40 mg/kg for 26 weeks showed that NOAEL dose was 40 mg/kg for both male and female rats. Repeat Oral dose Toxicity Study of buntanetap in male and female dogs giving 5, 10 and 20 mg/kg for 39 weeks showed that NOAEL dose was 20 mg/kg for both male and female dogs.

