#### 6.1. Randomization

Participants who have signed an informed consent and meet screening eligibility requirements will be randomly assigned to the active and placebo treatment groups at 1:1:1:1 ratio. The randomization methodology used is permuted block randomization.

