#### 7.8.2 Permitted Concomitant Medications

Use of the following medications is allowed only if the participants have been stabilized for at least 4 weeks before screening and will continue to be stable throughout the study:

- tricyclic antidepressants
- antipsychotics prescribed for any reason. However, the dosage must not exceed the following for these medications:
  - Quetiapine  $\leq$ 50 mg/day, risperidone  $\leq$ 1.5 mg/day, olanzapine  $\leq$ 5 mg/day, and aripiprazole  $\leq$ 10 mg/day

If the subject is on other antipsychotics besides the ones mentioned above, please consult the MM before screening the subject.

psychostimulants

Confidential Page 34 of 57

Discontinuation and/or change of any of the above medication during the course of the study is discouraged, however, if necessary, the site should consult with the Medical Director and Sponsor for further guidance.

This protocol allows concomitant treatment with anti-cholinesterase for 4 weeks or greater prior to screening.

If participants are taking any anticonvulsant medications used for epilepsy or mood stabilization, neuropathic pain indications, dosing must be stable for at least 4 weeks prior to screening.

Mood-stabilizing psychotropic agents, including but not limited to lithium, are permitted. Dosing must be stable for at least 4 weeks prior to Screening.

Use of short acting benzodiazepines and hypnotics for treatment on an as-needed basis for insomnia or daily dosing as anxiolytics is permitted but should be avoided for 8 hours before administration of cognitive tests. If sedating medication is given for any short-term use, then all cognitive assessments must be administered at least 24 hours after administration of the sedative.

At this time, there is no controlled clinical data available for anyone receiving SARS-CoV-2 (COVID19) vaccination while being treated with buntanetap. However, based on the intended mechanism of actions and currently available data for these vaccine candidates and for buntanetap, it is not believed that there are specific risks to consider in participants participating in this study who have received SARS-CoV-2 (COVID19) vaccination or who are planning to receive the vaccination. As such, SARS-CoV-2 (COVID19) vaccination is not prohibited. If appropriate, SARS-CoV-2 (COVID19) vaccination should be considered as a concomitant medication

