  - Oral, intravaginal, or transdermal combined (estrogen plus progestogen) hormonal contraception associated with inhibition of ovulation
  - Oral, injectable, or implantable progestogen-only hormonal contraception associated with inhibition of ovulation

Confidential Page 36 of 57

- Intrauterine device (IUD)
- Intrauterine hormone-releasing system (IUS)
- Bilateral tubal occlusion
- 7. Participants can provide written informed consent. If PI deems that participant cannot fully understand ICF to give consent, their legally authorized representatives (LARs) can provide written informed consent. Participants can comply with scheduled visits, and other study-related procedures to complete the study with the help of the study partner.
- 8. No evidence of current suicidal ideation or previous suicide attempt in the past 2 months as evaluated in the Columbia Suicide Severity Rating Scale nor suicidal behavior in the past 6 months as per investigator.
- 9. Stability of permitted medications for at least 4 weeks prior to screening.
  - a. Cholinesterase inhibitors and/or memantine medication
  - b. Anticonvulsant medications used for epilepsy or mood stabilization, neuropathic pain indications.
  - c. Mood-stabilizing psychotropic agents, including, but not limited to, lithium.
- 10. Adequate visual and hearing ability (physical ability to perform all the study assessments) as per investigator.
- 11. Good general health with no disease expected to interfere with the study as per investigator.

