8.2.7 Primary Analysis

The co-primary endpoints in this clinical trial are the change from baseline to Week 12 in ADAS-Cog11 score and the ADCS-CGIC score at Week 12 between buntanetap-treatment (pooling three treatment arms together) and placebo.

The statistical hypothesis to be tested for co-primary endpoint ADAS-Cog11 score is described as:

• Null Hypothesis (H0):

The difference in change in ADAS-Cog11 score from baseline to Week 12 between buntanetap-treatment (pooling three treatment arms together) and placebo = 0.

Alternative Hypothesis (H1):

The difference in change in ADAS-Cog11 score from baseline to Week 12 between buntanetap-treatment (pooling three treatment arms together) and placebo $\neq 0$.

The statistical hypothesis to be tested for co-primary endpoint ADCS-CGIC score is described as:

Null Hypothesis (H0):

The difference in ADCS-CGIC score at Week 12 between buntanetap-treatment (pooling three treatment arms together) and placebo = 0.

Alternative Hypothesis (H1):

The difference in ADCS-CGIC score at Week 12 between buntanetap-treatment (pooling three treatment arms together) and placebo $\neq 0$.

The two co-primary endpoints will be analyzed via MMRM. The model for the co-primary endpoint ADAS-Cog11 score will include treatment, timepoint, treatment-by-timepoint interaction as the fixed effects and baseline as the covariate. The Model for the co-primary endpoint ADCS-CGIC score will include treatment, timepoint, treatment-by-timepoint interaction as the fixed effects. The variance-covariance matrix will be assumed to be UN.

This analysis will be conducted after all participants have reached Week 12 or early withdrawal, whichever comes first. The primary analysis will be conducted in ITT. The mITT and PPS will be used to support the primary analysis.

Descriptive statistics per visit and change from baseline for each visit will be provided.

As the study is also designed to explore the effectiveness of three buntanetap-treatment dose levels on co-primary endpoints, similar MMRM will be applied comparing each buntanetap-treatment dose arm with placebo.

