8.4 Plasma Biomarkers and Pharmacokinetic Analysis

Biomarkers, including A β 42/40 ratio, pTau181, pTau217, GFAP, NFL and potentially TDP43, will be summarized descriptively for SAF.

Plasma concentration-time data for buntanetap will be listed and summarized descriptively (number of subjects (N), mean, geometric mean, median, SD, coefficients of variation (CV), minimum, and maximum) for the SAF.

Non-compartmental analysis of one analyte (buntanetap) in blood matrix concentrations will be performed using validated computer software Phoenix. Results will be tabulated and graphically displayed using Phoenix and appropriately interpreted by a PK Scientist. Calculations will be based on the actual sampling times recorded during the study. The following PK parameters will minimally be determined, as data permit:

- Area under the curve (AUC), including AUC_{0-10hr} and AUC_{0-inf}
- Maximum concentration (C_{max}) and time of maximum concentration (T_{max})
- Terminal half-life (t½)
- Systemic clearance (CL).

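### No planned analysis shows whether the buntanetap effect differs by background cholinesterase-inhibitor use, and chance imbalance in that use is left unadjusted

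*SAP*

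**What the plan says.** **Background treatment is allowed.** Protocol 7.8.2 states: "This protocol allows concomitant treatment with anti-cholinesterase for 4 weeks or greater prior to screening". Inclusion criterion 9 (Protocol 8.1) lists "Cholinesterase inhibitors and/or memantine medication" among the drugs that must be stable for at least 4 weeks before screening. SAP 8.2.11.2 repeats the anti-cholinesterase allowance.

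**Randomisation.** Protocol 6.1 says: "The randomization methodology used is permuted block randomization". No stratification factor is named there or in SAP section 5.

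**Models.** SAP 8.6 says: "Baseline value will be used as a covariate in the MMRM analyses for the co-primary endpoint ADAS-Cog11 score". No other covariate is listed. For the second co-primary, SAP 8.2.7 says: "The Model for the co-primary endpoint ADCS-CGIC score will include treatment, timepoint, treatment-by-timepoint interaction as the fixed effects". That model has no covariate at all.

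**Subgroups.** SAP 8.7 reads in full: "No subgroup analyses are planned for this study".

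**Use of the medication data.** The Schedule of Events has a concomitant medication review at every visit. SAP 8.2.11 tabulates medications by arm and for pooled buntanetap. The one extra drug-class listing, in SAP 8.2.11.3, is for anti-parkinsonian drugs.

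**Pharmacology.** Protocol 3.1 reports that "a metabolic product of buntanetap, N1-norposiphen demonstrated acetyl cholinesterase inhibitory activity". Protocol 3.2 ties the highest tolerated dose to levels of the N1 metabolite. SAP 8.4 describes a "Non-compartmental analysis of one analyte (buntanetap) in blood matrix concentrations".

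**The concern.** Each arm may contain both users and non-users of cholinesterase inhibitors. This is more than a routine request for subgroups, because the protocol describes a metabolite of the study drug that acts on the same enzyme as the background drugs. A 12-week cognitive effect could overlap with background treatment, or be independent of it as the protocol hypothesises.

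Two things are at stake. The first is interpretation. A pooled estimate averages over whatever mix was enrolled, and nothing planned separates the two groups. If the effect were confined to non-users, a weak pooled result would go unexplained. The second is adjustment. The comparison is 3:1 with about 70 evaluable placebo participants, and no model term absorbs a chance difference in user share.

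**Working it through.** **Inputs** (Protocol 6.2, SAP section 6): 210 pooled active and 70 placebo evaluable; ADAS-Cog11 delta 2.7; SD 6.0; two-sided 0.05; 12.5% dropout. The documents give no share of users, so f is an assumption, varied from 30% to 80%. Calculations treat Week 12 as a simple comparison of two means; baseline adjustment could narrow the intervals somewhat.

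**1. The plan's own figure.** SE = 6.0 × √(1/210 + 1/70) = 0.83. Power = Φ(2.7/0.828 − 1.96) = 90.3%, and 280/(1 − 0.125) = 320. Both stated values reproduce.

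**2. Chance imbalance in user share.** SD = √[f(1 − f)(1/210 + 1/70)].
- f = 0.5: √(0.25 × 0.01905) = 6.9 percentage points
- f = 0.7: √(0.21 × 0.01905) = 6.3 percentage points

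A gap of 13 points is therefore about 2 SD.

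**3. What such a gap does to the estimate.** Assume that users and non-users differ by 1 to 2 points in 12-week change (not in the documents). A 13-point gap moves the treatment difference by 0.13 × 1 = 0.13 to 0.13 × 2 = 0.26 points, or 0.16 to 0.31 of the 0.83 SE.

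**4. Pooled power if the 2.7-point effect exists only in non-users.** The pooled effect becomes 2.7(1 − f).

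| f | pooled effect | power |
|---|---|---|
| 0.3 | 1.89 | 63% |
| 0.5 | 1.35 | 37% |
| 0.7 | 0.81 | 16% |

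**5. Precision of a by-use analysis.** With n placebo participants in a stratum and 3n active, the variance is v(n) = 36 × (1/n + 1/(3n)) = 48/n. The stratum half-width is 1.96√v. The interaction SE is √[v(70f) + v(70(1 − f))], and its power is for a 2.7-point difference between strata.

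| f | half-width, users | half-width, non-users | interaction SE | interaction half-width | power |
|---|---|---|---|---|---|
| 0.3 | 2.96 | 1.94 | 1.81 | 3.54 | 32% |
| 0.5 | 2.30 | 2.30 | 1.66 | 3.25 | 37% |
| 0.7 | 1.94 | 2.96 | 1.81 | 3.54 | 32% |
| 0.8 | 1.81 | 3.63 | 2.07 | 4.06 | 26% |

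The interaction detectable with 80% power is about 4.6 points at f = 0.5 and 5.8 points at f = 0.8.

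For ADCS-CGIC, scaling by 0.5/6.0 gives interaction half-widths of 0.27 to 0.34, against a design difference of 0.23.

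**6. Exposure.** The N1 level of about 10 to 15% of parent drug in plasma (Protocol 3.2) was seen at 4 × 60 = 240 mg/day. That is 240/30 = 8 times this trial's top daily dose.

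**The case against.** The strongest reply is that nothing here damages the primary test. Randomisation balances background use in expectation, the pooled estimate is a valid average over the enrolled mix, and the test's error rate already allows for chance imbalance. By step 3, even a 2 SD gap would move the estimate by under a third of an SE on the assumed prognostic differences. All of this stands. Adjustment is a gain in precision and protects against an unlucky draw; it does not correct an error.

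The pharmacology also cuts both ways. Protocol 4.1 says that buntanetap itself has no such activity, that phenserine has about 10 to 20 times more acetylcholinesterase inhibition in vivo than the metabolite, and that target effects occur at levels 8 to 16 times below cholinomimetic ones. A reader might infer that any benefit would be cholinergic; the documents do not support that. They do not exclude a contribution either, since Protocol 4.1 attributes the 8-to-16-fold margin to preliminary studies and SAP 8.4 names only the parent drug as analyte. A separate PK SAP, not supplied, may say more.

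Finally, a by-use split is likely to be inconclusive. That stands too: the within-stratum intervals look usable, but a claim that the effect sits in one group rests on the interaction, whose half-width exceeds the whole design effect.

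**Conclusion.** The gap is real but limited. Background use is permitted and recorded, yet no stratification factor is named, neither co-primary model includes it, and no planned analysis separates users from non-users.

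A reader might go further and say that the trial cannot tell whether benefit exists on top of standard drugs, or that background use is ignored. The documents do not support either. Use is restricted by a stability rule, reviewed at each visit and tabulated by arm, so imbalance will be visible and a post hoc split is possible. What is missing is a split fixed in advance. A stratification factor could also sit in a randomisation plan that was not supplied.

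The size depends on the unknown user share. Imbalance has an SD of 6.3 to 6.9 points at 50 to 70% users. Interaction power is 26 to 37% for a full 2.7-point difference at 30 to 80% users, so only a very large difference would be clear. The case for acting is that the question is foreseeable, the data are already collected, and a prespecified answer is more credible than a discretionary one.

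**What to change.** Make these changes before unblinding, using one definition throughout: cholinesterase-inhibitor use at baseline, yes or no. Memantine-only participants count as non-users, because the metabolite rationale concerns acetylcholinesterase.

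1. **SAP 8.6 and 8.2.7:** add baseline cholinesterase-inhibitor use as a fixed effect in both co-primary MMRMs. Update the model equations in SAP 8.2.3, say whether the secondary-endpoint models follow, and record the change in SAP 8.1.
2. **SAP 8.7:** replace the sentence with one prespecified descriptive analysis. For each co-primary, give the pooled buntanetap minus placebo difference at Week 12 with its 95% CI in users and in non-users, plus the interaction estimate with its CI. Make no alpha claim.
3. **Same section:** state the expected precision from steps 4 and 5 of the working, so that a null interaction is not read as evidence of a uniform effect.

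The cost is one degree of freedom, a few extra model runs, and imprecise subgroup estimates that must be labelled descriptive. No new data are needed, and alpha and eligibility do not change. Stratifying randomisation is no longer possible at the SAP stage. If the blind has already been broken, the same analyses should be reported as post hoc.

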8.8 Handling of Dropouts, Intercurrent Events, and Missing Data

In case of incomplete dates, the following approach will be used:

- If only the day is missing and the month and year are different from the month and year of the
 index date, the day will be imputed with 1. In case the month and year are the same as the
 index day the missing day will be imputed with the last day of the month.
- · In case of missing months, they will be imputed
 - o with July if the year is not the same as the year of the index date
 - with the following month as the month of the index date if the year is the same as the year of the index date.

If not indicated otherwise in case of completely missing dates no imputation will be done.

For co-primary endpoint ADAS-Cog11, if there are 3 or less missing item scores at a visit, the missing item score will be imputed using the group mean score of that item within the same treatment group at the same visit. If there are more than 3 item scores missing, the total score will be set as missing. The same MMRM analysis as the one applied to the primary analysis will be fitted as a sensitivity analysis.

The MMRM analysis of the two co-primary endpoints assumes that data are missing at random (MAR). The analysis will be conducted in ITT set and subjects will be analyzed as randomized. ITT subjects discontinue from the study for any reason without completing the study are considered intercurrent events. To assess the robustness of this MAR assumption, a conservative control-based multiple imputation method based on missing not at random (MNAR) assumption will be applied to impute missing data arising from intercurrent events for the two co-primary endpoints analyses. In this MNAR approach, subjects who do not complete the study, missing data will be imputed by observed data obtained from the placebo group using multiple imputation with Markov Chain Monte Carlo (MCMC) simulation method for each treatment separately. For the co-primary endpoint ADAS-Cog11 score, the variables for the imputation model will include ADAS-Cog11 score at baseline, Week 6, and Week 12. The ROUND, MINIMUM and MAXIMUM options will be utilized to ensure imputed values are clinically plausible integers (0 - 70). For the co-primary endpoint ADCS-CGIC score, the variables for the imputation model will include ADCS-CGIC score at Week 6 and Week 12. The ROUND, MINIMUM and MAXIMUM options will be utilized to ensure imputed values are clinically plausible integers (1 -7). Approximately 50 datasets will be imputed and the same MMRM analysis as the one applied to the primary analysis will be fitted. The results from these 50 analyses will be combined using Rubin's rule to construct the treatment estimates from the parameter estimates and associated standard errors. The difference of the treatment means (active minus placebo) will be presented with the associated standard error and two-sided 95% confidence interval. The imputation will be performed for the two co-primary endpoints separately. Two random seed numbers will be selected for the multiple imputation procedure and will be retained.

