Statistical Analysis Plan Version 2.0, 27 February 2024

1 Abbreviations

 $\begin{array}{ll} \alpha SYN & Alpha-synuclein \\ A\beta & Amyloid \ beta \end{array}$

AD Alzheimer's disease

ADAS-Cog Alzheimer's Disease Assessment Scale-Cognitive Subscale

ADCS-ADL Alzheimer's Disease Cooperative Study—Activities of Daily Living Scale

ADCS-CGIC Alzheimer's Disease Cooperative Study—Clinical Global Impression of

Change

AE Adverse Event

APP Amyloid β Precursor Protein AR(1) First-order Autoregressive

ATC Anatomical Therapeutic Chemical

AUC Area under the curve

C_{max} Maximum plasma and CSF concentration

CI Confidence interval

CL Clearance

CM Concomitant medication
CSF Cerebrospinal Fluid
CSP Clinical Study Protocol

C-SSRS Columbia Suicide Severity Rating Scale

CV Coefficients of variation

DSMB Data Safety Monitoring Board
DSST Digital Symbol Substitution Test

ECG Electrocardiogram

eCRF Electronic Case Report Form

ES Enrolled set

FDA Food and Drug Administration
GFAP Glial Fibrillary Acidic Protein

IC Informed Consent

IMP Investigational Medicinal Product iSAP interim Statistical Analysis Plan

ITT Intent-to-Treat set
LSM Least Square Mean
MAR Missing at Random

MCMC Markov Chain Monte Carlo

MedDRA Medical Dictionary for Regulatory Activities

mITT Modified Intent-to-Treat set

MMRM Mixed Model for Repeated Measures

MMSE Mini-Mental State Examination

MNAR Missing Not at Random NFL Neurofilament Light Phosphorylated tau p-tau PDParkinson's disease PΚ Pharmacokinetic PPS Per-protocol set PT Preferred Term QD Once a Day

SAE Serious Adverse Event
SAF Safety analysis set
SAP Statistical Analysis Plan
SD Standard Deviation
SOC System Organ Class

TEAE Treatment-Emergent Adverse Event

T_½ Half-life tau Tau protein

TDP-43 TAR DNA-binding Protein 43 t_{max} Time to peak drug concentration

TOEPH Heterogeneous Toeplitz

UN Unstructured

WHO World Health Organization

2 Document Version History

Version Number	Version date	Section(s) Updated	Change since previous version (with reason)
Final 1.0	16-JAN-2024	All	Final version
Final 2.0 Amendment	27-FEB-2024	Section 8.8	Missing data algorithm was added on item scores of co-primary endpoint ADAS-Cog11 as a sensitivity analysis

3 Introduction

This Statistical Analysis Plan (SAP) is based on Clinical Study Protocol (CSP) Version 3.1, dated September 25, 2023. In the case where there is a difference between the protocol and the SAP, the SAP will be the ruling document.

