The objective of this study is to assess efficacy and safety of buntanetap in participants with mild to moderate AD. We only tested 80 mg once daily (QD) in Phase 2a study in AD participants. During the dose-finding Phase 2a PD study, a dose-response curve between 0 and 80 mg QD was observed with 10 and 20 mg QD showing the best benefit. Therefore, we want to do a similar dose-ranging trial to test the efficacy of 7.5 mg, 15 mg and 30 mg QD buntanetap.

4 Study Objectives and Endpoints

Objective Endpoint

Primary

The primary objective is to assess efficacy and safety of buntanetap in participants with mild to moderate AD.

1. Alzheimer's Disease Assessment Scale-Cognitive Subscale 11 (ADAS-Cog 11)

Change in ADAS-Cog 11 from Baseline to Week 12.

ADAS-Cog 11 is an 11-item score measuring cognitive functions and non-cognitive functions such as mood and behavior. Total scores range from 0-70, with higher scores indicating greater cognitive impairment.

2. Alzheimer's Disease Cooperative Study-Clinical Global Impression of Change (ADCS-CGIC)

ADCS-CGIC is a validated categorical measure of change in the participant's clinical condition between baseline and follow-up visits. It measures whether the effects of active treatment are substantial enough to be detected by a skilled and experienced clinician on the basis of a clinical interview and examination. It relies on both direct examination of the participant and an interview of the study partner. A skilled and experienced clinician who is blinded to treatment assignment rates the participant on a 7-point Likert scale, ranging from 1 (marked improvement) to 7 (marked worsening). Lower scores indicate better improvement.

3. Safety and tolerability

- Adverse events (AE)
- Severity of AEs
- Drug related AEs
- · AEs leading to study discontinuation
- Electrocardiogram (ECG) findings
- Clinical laboratory test results
- Vital sign measurements
- Physical examination findings

Objective

ANVS-22002

Endpoint

Secondary

Assess improvement on AD participants' daily living and cognitive functions

Alzheimer's Disease Cooperative Study-Instrumental Activities of Daily Living Scale (ADCS-ADL)

The ADCS-ADL is a 23-item inventory developed as a rater-administered questionnaire answered by the participant's study partner. The ADCS-ADL measures both basic and instrumental activities (instrumental activity items 6a, 7-23) of daily living by participants with a lower score indicating greater severity.

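### The ADAS-Cog11 item-level sensitivity analysis fills missing items with the participant's own arm mean, so it is least reliable when missingness follows severity and differs between arms

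*SAP*

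**What the plan says.** SAP section 4 describes an 11-item scale: "Total scores range from 0-70, with higher scores indicating greater cognitive impairment". SAP 8.8 sets the rule for incomplete forms. It applies "if there are 3 or less missing item scores at a visit", and then "the missing item score will be imputed using the group mean score of that item within the same treatment group at the same visit". Beyond that limit, "If there are more than 3 item scores missing, the total score will be set as missing".

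The role of the rule is stated twice. SAP 8.8 ends the paragraph with "The same MMRM analysis as the one applied to the primary analysis will be fitted as a sensitivity analysis", and the version history for SAP 2.0 records: "Missing data algorithm was added on item scores of co-primary endpoint ADAS-Cog11 as a sensitivity analysis".

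The rule takes nothing from the participant's answered items, baseline or other visit. It does not exclude the baseline visit, so the baseline covariate in the MMRM can be filled in the same way. The control-based multiple imputation, also in SAP 8.8, works on total scores of participants who do not complete the study. It does not deal with partly completed forms, so the arm-mean fill is the only stated check on them.

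**The concern.** Protocol 8.1 admits participants with MMSE 14 to 24, so severity varies widely within each arm. In such a population an item may well be missing because the person could not do it. The arm mean then gives an impaired participant an average score on that item, and the total looks better than it should. A mildly affected participant with a missing item is made to look worse.

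If this happens equally in all arms, the errors largely cancel in the treatment difference. If item missingness depends on severity and its rate differs by arm, they do not cancel, and the difference moves in whichever direction the imbalance runs. A sensitivity analysis for incomplete forms is there to show whether informative missingness matters, and this one is distorted in that case. Because each filled value counts as observed, the analysis also understates its uncertainty.

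**Working it through.** **Inputs from the documents.** Eleven items, range 0 to 70, at most 3 items filled (SAP 4 and 8.8). Planned difference 2.7, SD 6.0, 210 pooled active versus 70 placebo, 90% power, 12.5% dropout (SAP 6).

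**Assumptions.** The documents give no item maxima, no between-person SD of the total score and no expected rate of missing items. I assume equal item weights, a total SD of 6 to 9, and the missingness rates shown below.

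**The plan's own figure.**
- Standard error of the difference: 6.0 x sqrt(1/210 + 1/70) = 0.83.
- Power: 2.7/0.828 - 1.96 = 1.30, which gives 90.3% against the stated 90%.
- Randomized: 280/0.875 = 320, as stated.

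**Shift in one person's total.** Let D be the person's distance from the arm mean total. Shift = (k/11) x D.
- k = 1: 0.09 x D; k = 2: 0.18 x D; k = 3: 0.27 x D.
- At D = 10 the shift is 0.9, 1.8 and 2.7 points for k = 1, 2 and 3.
- At D = 5 with k = 3 it is 1.4 points.
- If three items carried 15% to 43% of the total instead of 27%, the D needed for a 2.7-point shift would run from 18 down to 6.3.

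**Shift in the treatment difference.** An arm's mean moves by f x (3/11) x D, where f is the share of the arm with three items missing and D is their average distance from the arm mean. The treatment difference moves by the gap between arms. Suppose missingness falls on the most impaired quarter, whose mean lies 0.318/0.25 = 1.27 SD above the arm mean, with f = 5% in one group and 15% in the other (a gap of 0.10):
- Total SD 6: D = 7.6, so 0.10 x (3/11) x 7.6 = 0.21.
- Total SD 9: D = 11.4, so 0.10 x (3/11) x 11.4 = 0.31.
- Baseline SD 9 plus change SD 6, so Week 12 SD = sqrt(81 + 36) = 10.8: D = 13.7, so 0.10 x (3/11) x 13.7 = 0.37.

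**Simulation.** Settings: 210 versus 70, true difference 2.7, baseline SD 9, change SD 6, three items deleted at random from each affected person, ANCOVA, 400 runs per case.

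| Missingness | Arm-mean fill | Prorating |
|---|---|---|
| Balanced across arms, 5% or 10%, random or in the worst quartile | moves by about 0.01 or less | moves by about 0.01 or less |
| Worst quartile, 5% active / 15% placebo | about 2.3 to 2.4 | about 2.7 |
| Worst quartile, 15% active / 5% placebo | about 3.0 to 3.1 | about 2.7 |
| Worst quartile, active arms only, 5% / 10% | benefit overstated by 0.2 / 0.4 | unchanged |

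The ranges come from repeat runs that differed in detail. With total SD 6, the 5%/15% case moved by about 0.2. With 2% versus 4% affected, the estimate moved by about 0.1.

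**When the missing items are the person's own worst ones** (SD 9, 5% versus 15%), the arm-mean fill moves the difference by about 0.65 to 0.68 and prorating by about 0.45. Prorated totals remain about 4.8 points too low per affected person.

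**The case against.** The strongest objection is that this is a sensitivity analysis only. The co-primary tests and the gatekeeping sequence do not use the filled totals. That stands. A reader might infer from SAP 8.8 that the co-primary ADAS-Cog11 score is built with arm means, but the closing sentence of that paragraph and the version history both say otherwise.

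A reader might also set the 2.7-point shift in one person's total beside the planned effect of 2.7 and conclude that the rule could create or erase the whole effect. That compares one person's score with a difference between group means. The 2.7 is reached only with three items missing and about 10 points' distance; with one item missing it takes about 30 points. The treatment difference moves only by the share affected times that shift, net between arms.

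The 5% versus 15% case is also demanding: three items missing in every affected person, all of them among the more impaired, and a threefold imbalance between blinded arms. Even then 0.4 points is about half a standard error (0.4/0.83). The documents give no sign of such an imbalance. This limits the size of the concern. It does not answer it, because a check on informative missingness should hold up when missingness is informative.

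Finally, prorating is not a complete cure. It is unbiased when random items are lost, but under the mechanism that causes the worry it removes only about a third of the bias (0.65 to 0.45). That stands, and the fix allows for it.

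**Conclusion.** The concern holds for the sensitivity analysis alone. The arm-mean fill ignores the participant's severity, uses treatment assignment, and enters the model as if observed. With random or balanced item missingness it does no material harm to the estimated difference. With missingness concentrated in the more impaired and unequal between arms, it moves the estimate by roughly 0.2 to 0.4 points from a true 2.7. This rests on assumed rates of 5% versus 15%, three items missing, equal item weights and a total SD of 6 to 9. The shift is larger, about 0.65, if the missing items are the ones the person could not do.

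The direction depends on which arm has more missing items, so the documents do not support a claim that the rule favours buntanetap. Nor do they support a claim that the primary result is biased by it. What they do leave open is how the primary analysis treats a form with one to three missing items, since no rule is given. The change is worth making because it is cheap and this is the only check on partly completed forms.

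**What to change.** In SAP 8.8, replace the arm-mean fill with a within-person rule that does not use treatment, and keep the 3-item limit. Two options:

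- prorate the total from the participant's answered items, scaled by the maximum points of those items; or
- impute the missing item from the person's other items and their own score on that item at the adjacent visit, preferably by multiple imputation so that the filled value is not treated as observed.

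If the eCRF records that an item was missing because the participant could not do it, add a run that scores those items at their worst value. The documents do not show whether this reason is collected. It would also help to say in one line how the primary analysis scores a form with one to three missing items, and to report the number of such forms by arm and visit.

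The cost is two or three sentences in SAP 8.8 and a small programming change, to be settled before unblinding. The drawback of prorating is its assumption that items are roughly proportional to overall severity. It also leaves part of the bias when the missing items are the person's worst, which is why the worst-score run belongs beside it.
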